- Number of adults in active HIV care in two largest clinics in each district
- HIV prevalence
- Incidence of IPT uptake
- Incidence of HIV-associated TB disease

We will also provide these summary measures by arm. We will additionally provide descriptions of secular events and non-study activities that are expected to impact study outcomes.

2 Primary outcome: IPT uptake

The primary endpoint is “IPT uptake”: the rate at which eligible HIV-positive adults receive an IPT prescription in health facilities overseen by DHOs participating in the SEARCH-IPT trial. This endpoint will be measured over 8 quarters (starting Q1-2019 in the Southwest and in Q2-2019 in the East and East-Central) among adults in active HIV care in two clinics in each district in the trial. These clinics were selected based on size, generally the biggest, and are assumed to be representative of the overall district. (This assumption of generalizability may or may not be reasonable in smaller and more rural districts.)

Data source: For each *clinic*, aggregate data on the total number of IPT starts and the total number of adults in active HIV care *in each quarter* will be extracted from the Ministry of Health HMIS database. Data on IPT initiation are available by sex, and data on adults in active care are available by sex and 1st/2nd/3rd line ARV regime. Primary analyses will pool over sex and ARV regime. Secondary analyses will be stratified on sex.

Missing data: There is no reason to believe data will be differentially captured by arm. Additionally, we are unable to differentiate between missing data on IPT prescriptions and simply 0 prescriptions for that clinic-quarter. Therefore, if data are missing on IPT prescriptions for a given clinic-quarter, we will assume there were 0 starts in that clinic-quarter; this will provide a lower bound on the total IPT starts for that clinic. However, if for a given clinic, data on IPT prescriptions are missing for all quarters, we will exclude that clinic.

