Likewise, there is no way to differentiate between missing data on the number of patients 2nd/3rd line ARV regimens or simply 0 participants on those lines. If data on the number of patients on 2nd or 3rd line ARV regimen are missing, we will assume that 0 patients are on those lines for that clinic-quarter. We do not anticipate data on the active care size to be completely missing for a given clinic-quarter; if this happens, we will estimate the clinic-quarter active care size by averaging the size in the prior clinic-quarter with the size in the subsequent clinic-quarter.

Incidence rate calculations: Because the number of adults in HIV care changes over time and the probability of starting IPT is not uniform over the 8 quarters of follow-up, we focus on estimation and inference of the incidence rate of IPT initiation, as opposed to the cumulative incidence. For each clinic, we will determine the total number of IPT starts and the total person-time-at-risk of IPT initiation (described below) over the two-year follow-up period. In primary analyses, we will calculate the district-level incidence rate as the total starts in a district (summed over the 2 clinics) divided by the total person-time-at-risk for that district (again summed over the 2 clinics). In secondary analyses, we will calculate the district-level incidence rate by averaging the clinic-specific incidence rates within each district.

Because data for each clinic-quarter are only available at the aggregate-level, we will take the following approach to calculating the person-time-at-risk (PT). In line with standard practice [3], we will assume that IPT initiations occur uniformly in each clinic-quarter. In primary analyses, we will also assume that all who started IPT during follow-up remain in active HIV care for the remainder of follow-up. While the latter assumption is supported by prescribing practices (i.e.,

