to patients who are stable in care), we will conduct two sensitivity analyses. In the first, we will assume that 97.5% of persons who previously started IPT remain in active care at the same clinic from quarter-to-quarter. In the second, we will assume that 0% of persons who previously started IPT remain in active care from quarter-to-quarter. The second sensitivity analysis is expected to be extremely conservative and will provide a lower bound in the estimated incidence rates. Altogether, PT for each clinic-quarter will be calculated as the quarter-specific number in active HIV care minus half the IPT starts in that quarter and X% of the previous IPT starts, where X% = 100% in the primary analysis, 97.5% in the first sensitivity analysis, and 0% in the second sensitivity analysis. The resulting incidences rates will be converted from being in ‘clinic-quarters’ to ‘person-years’ for ease of interpretation.

In a secondary analysis, we will calculate the two-year, cumulative incidence of IPT initiation as the total number of IPT starts, divided by the average active care size over follow-up. As before, we will calculate the district-level cumulative incidence in two ways: (1) the total starts in a district (summed over the 2 clinics) divided by the total active care size for that district (again summed over the 2 clinics); and (2) by averaging the clinic-specific cumulative incidences within each district. We will also report total starts by arm.

All analyses will assume that all adults in active HIV care are eligible for IPT at the beginning of follow-up (Q1-2019 in the Southwest and Q2-2019 in the East/East-Central). By randomization, the number in active HIV care and the number who had previously started IPT should be balanced between arms.

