If data on the number of patients on 2nd or 3rd line ARV regimen are missing, we will again assume that 0 patients are on those lines in that district-quarter. We do not anticipate data on the active care size to be completely missing for a given district-quarter; if this happens, we will estimate the district-quarter active care size by averaging the size in the prior district-quarter with the size in the subsequent district-quarter.

Incidence calculations: Because the number of persons in active HIV care changes over time and the rate of TB disease diagnosis may not be uniform over the 8 quarters of follow-up, we again focus on the incidence rate, as opposed to the cumulative incidence. For each district, we will estimate the TB incidence rate as the total number of cases divided by the total person-time-at-risk (PT) over the two-year follow-up period. As before, when calculating the incidence rate, we will assume events (here, TB disease diagnoses) occur uniformly in each district-quarter and that a fixed proportion of prior TB cases remain in active care within the same district from quarter-to-quarter. Then in each district-quarter, the PT will be calculated as the quarter-specific number in active HIV care minus half the cases occurring in that quarter and X% of the previous cases, where X% = 100% in the primary analysis, 97.5% in the first sensitivity analysis, and 0% in the second sensitivity analysis. The resulting incidences rates will again be converted from being in ‘clinic-quarters’ to ‘person-years’ for ease of interpretation. In secondary analyses, we will estimate the district-specific cumulative incidence of TB as the total number of cases divided by the average active care size. We will also report total number of TB diseases diagnoses by arm.

All analyses will assume all persons in active HIV care are at risk of TB disease at the beginning of follow-up (Q1-2019 in the Southwest and Q2-2019 in the East/East-Central). By randomization, the number in active HIV care and the number who had previously been diagnosed with TB disease should be balanced between arms.

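### The 97.5% sensitivity analysis for IPT starters leaving care deducts a flat 97.5% of earlier starts, so it applies only about a third of the quarterly attrition it assumes; the effect on the rate ratio is small

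*SAP*

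**What the plan says.** SAP section 2, under the incidence rate calculations, has only aggregate clinic-quarter counts, so it must assume what becomes of people after they start IPT. The primary analysis assumes that "all who started IPT during follow-up remain in active HIV care for the remainder of follow-up". Two sensitivity analyses relax this. One supposes a small loss of starters: "97.5% of persons who previously started IPT remain in active care at the same clinic from quarter-to-quarter". The other goes to the opposite extreme: "0% of persons who previously started IPT remain in active care from quarter-to-quarter".

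The calculation is then given in a single rule. Person-time in a clinic-quarter is the number in active care "minus half the IPT starts in that quarter and X% of the previous IPT starts". The values of X are 100%, 97.5% and 0% for the primary and the two sensitivity analyses in turn. On duration: "This endpoint will be measured over 8 quarters".

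SAP section 3 carries the same scheme over to TB, with person-time equal to the number in care "minus half the cases occurring in that quarter and X% of the previous cases" and the same three values of X.

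**The concern.** The first sensitivity assumption is a retention rate per quarter. The contrast with the primary assumption, which is worded to the end of follow-up, supports that reading. A per-quarter rate compounds: someone who started d quarters ago is still in care with probability 0.975^d. The formula has no exponent, recursion or carried-forward pool. It applies one fraction to all earlier starts, recent or old.

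X=100% and X=0% give the same answer flat or compounded, so only the intermediate analysis is affected. There the flat rule deducts starters who, on the stated assumption, have already left. Person-time comes out too small and the rate too high, more so where more people have started. If the intervention works, this holds the sensitivity rate ratio closer to the primary one than the stated assumption implies. What is at stake is whether a pre-specified robustness check does what it says.

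**Working it through.** **Inputs.** Retention of 97.5% per quarter, the person-time formula and 8 quarters of follow-up: SAP section 2. Planning rates of 22 per 100 person-years and an absolute increase of 10: SAP section 6.3. TB incidence of 200 per 100,000 person-years and a 40% reduction: protocol section 6.5.2.2. The SAP gives no result for this sensitivity analysis, so there is none to reproduce.

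**Check that 22 vs 32 is the planned contrast.** The unmatched cluster formula for rates, one-sided 5%, 80% power, k = 0.25 and 21,500 person-years per group, gives

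c = 1 + (1.645 + 0.842)² × [(0.22 + 0.32)/21,500 + 0.25² × (0.22² + 0.32²)] / 0.10² = 6.84.

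That rounds up to the SAP's 7 groups per arm, so the reading is right.

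**Attrition delivered and attrition stated.** At d quarters after a start, the flat rule has 2.5% gone at every d. The stated assumption has 1 − 0.975^d gone:

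| d | 1 | 2 | 3 | 4 | 5 | 6 | 7 |
|---|---|---|---|---|---|---|---|
| Stated loss, % | 2.5 | 4.9 | 7.3 | 9.6 | 11.9 | 14.1 | 16.2 |

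With equal starts each quarter, lag d occurs 8 − d times, so there are 28 start-by-later-quarter pairs. Per unit of quarterly starts:

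- Flat: 28 × 0.025 = 0.70 person-quarters.
- Compounded: Σ (8 − d)(1 − 0.975^d) = 0.175 + 0.296 + 0.366 + 0.385 + 0.357 + 0.282 + 0.162 = 2.02 person-quarters.
- Share delivered: 0.70 / 2.023 = 34.6%.

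Mean retention of earlier starters is therefore 97.5% under the flat rule and 1 − 2.023/28 = 92.8% under the stated assumption.

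The share depends moderately on when starts occur: 31–33% with a 3- to 10-fold peak in follow-up quarter 2, about 34.5% with that peak in quarter 3, 32% front-loaded and 41% back-loaded. If loss began only in the second quarter after a start, the share would be 0.70/1.357 = 52%. The SAP's formula already removes 2.5% in the first following quarter, so 34.6% is the like-for-like figure.

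**Effect on the rate ratio.** Assumptions: a constant 1,000 in care, starters leaving at 2.5% per quarter, and leavers replaced by IPT-naive patients. With quarterly hazard h (annual rate/4), starts_q = h × (1,000 − retained_q − starts_q/2) and retained_q = 0.975 × (retained_{q−1} + starts_{q−1}). Each person-time rule is then applied to the same starts:

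| Rule | 22 vs 32: rates | RR | 40 vs 80: rates | RR |
|---|---|---|---|---|
| X=100% | 22.34 / 32.76 | 1.466 | 41.23 / 85.87 | 2.08 |
| Flat 97.5% | 22.23 / 32.50 | 1.462 | 40.81 / 83.90 | 2.06 |
| Compounded 97.5% | 22.00 / 32.00 | 1.455 | 40.00 / 80.00 | 2.00 |
| X=0% | 18.47 / 24.87 | 1.347 | 29.27 / 44.24 | 1.51 |

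Compounding returns the true rates by construction. The 40 vs 80 case is illustrative and does not come from the documents.

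**Effect of an early peak.** Here starts are instead fixed so that X=100% gives exactly 22 and 32. The flat and compounded ratios are 1.451 and 1.446 with equal starts (gap 0.006), 1.451 and 1.444 with a five-fold peak in quarter 3 (gap 0.007), and 1.451 and 1.443 with that peak in quarter 2 (gap 0.008). The 100-day push in Q3-2019 falls in follow-up quarter 3 in the Southwest and quarter 2 in the East and East-Central.

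**TB.** At 200 vs 120 per 100,000 person-years the ratio is 0.59998 flat and 0.60000 compounded.

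**The case against.** The strongest reply concerns weight. Three parts of it stand.

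- At the planning rates, the log difference between flat and compounded is ln(1.462/1.455) ≈ 0.005. With k = 0.25 and 7 groups per arm, the between-cluster standard error of the log rate ratio is roughly √(2 × 0.0625/7) = 0.134, ignoring Poisson error. The discrepancy is about 4% of one standard error at 22 vs 32 and about 20% at 40 vs 80.
- Correct compounding also stays close to the primary result: 1.466 becomes 1.455. A loss of 2.5% per quarter has little leverage at these rates, however it is coded.
- The benchmark is assumed. The SAP's retention is at the same clinic, so leavers may include transfers, and patients transferring in after IPT elsewhere would wrongly count as at risk. That would offset some of the overstatement.

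It can also be said that the formula is a verbal summary and the code may already update a retained pool. It may, but the SAP does not say so, and a reader programming from the text would code the flat rule.

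Four stronger inferences are tempting, and the documents do not support them. First, a reader might infer that the trial's main result is compromised; the primary analysis uses X=100%, where the two rules coincide. Second, a reader might infer that this is the only usable check on retention. SAP section 2 also specifies the X=0% bound and a two-year cumulative incidence analysis that deducts no earlier starters. Third, person-time can turn negative at very high uptake, but it does so first under X=100%, which makes it a separate question about the primary formula. Fourth, the same wording in section 3 might suggest that TB results are at risk; with so few cases the difference is nil.

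**Conclusion.** The rule as written is wrong for its own assumption, and the effect is small. The first sensitivity analysis states a per-quarter loss and applies a one-time loss, delivering about a third of the attrition it describes (34.6% with equal quarterly starts; 31–41% across the patterns tried). At the SAP's planning rates this moves the sensitivity rate ratio by 0.007 (1.462 to 1.455). The gap widens with higher uptake, or when starts are concentrated early.

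The rate-ratio figures rest on constant care size and replacement of leavers by IPT-naive patients. The mismatch itself needs neither assumption. The compounded estimate lies between the X=100% and X=0% results that the SAP already reports, and nothing here suggests that a trial conclusion would change.

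**What to change.** In the 97.5% analysis of SAP section 2, replace the deduction of 97.5% of earlier starts with a retained pool: retained_1 = 0 and retained_q = 0.975 × (retained_{q−1} + starts_{q−1}). This equals the sum over earlier quarters j of starts_j × 0.975^(q−j). Leave X=100% and X=0% unchanged. Use the same recursion for TB cases in section 3, for consistency only.

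If a one-time loss was what was meant, reword the assumption as 2.5% ever lost, so that text and formula agree.

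The cost is one line of SAP text and one of code, with no new data. If the change follows unblinding, record it in the SAP's history of changes as a correction to match the stated assumption. The 97.5% estimate will move slightly further from the primary one.

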5.3.1. SPIRIT-1: The Teaching Collaborative

Study staff will form up to 7 mini-collaboratives directly from the intervention groups of 4-7 DHOs each (Figure 1), along with any support staff the DHOs may bring, including the District TB Supervisor. Each mini-collaborative of DHOs will be led by an opinion leader (“coach” - selected by the SPIRIT investigators) with HIV and TB expertise, to spread new scientific knowledge about IPT and the clinical ability to rule out TB, and to facilitate discussion between DHOs. Additional training at the Teaching Collaboratives (and the Reporting Collaboratives – see below) may include skills, such as business and management training provided by business leaders, that aim to assist the DHOs and the District TB Supervisors, in overseeing any new or ongoing initiatives to improve IPT implementation. This additional training may also act to incentivize DHOs and District TB Supervisors to continue engaging in SPIRIT intervention mini-collaborative meetings (both Teaching and Reporting) for their personal and professional development.

The rationale for this approach is that research on the link between implementation and program outcomes show that outcomes may not be achieved by didactic training alone and that “coaching” is critical for success.³⁸ Coaching can facilitate: a) “buy in” from participants; b) sharing of best practices; and c) a productive environment for accountability. By creating a collaborative, the SPIRIT intervention seeks to enable a group to form bonds so that perspectives in favor of IPT can spread within the group.³⁹

Implementation: We will hold these meetings twice a year for three years during the SPIRIT intervention, with 1-2 additional meetings in the first year of the intervention period. At each meeting, the group may generate ideas about how best to implement the SPIRIT intervention (see 5.3.2. SPIRIT-2 below), and to discuss lessons learned from the use of novel components of the intervention. We will also be communicating with the DHOs and District TB Supervisors with phone calls using a pre-specified script up to two times between each of these meetings to discuss progress toward IPT implementation.

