The primary outcome of IPT uptake is the rate at which eligible HIV-infected adults who receive a prescription for INH at a health facility overseen by DHOs participating in the SPIRIT trial. IPT initiation will be measured among the two largest clinics in each district and over the 24-month period, beginning 12 months after the intervention start in each pair-matched DHO group. The 12-month lead-in is to account for ramp-up of the SPIRIT intervention and for INH stock-outs. The denominator of this rate is the person-time-at-risk of starting IPT, accounting for prior starts and other changes in the active care population. The numerator is the number of HIV-infected adults prescribed INH. In other words, the primary outcome is the incidence rate of IPT prescriptions among eligible HIV-positive patients. The primary outcome will be compared between SPIRIT intervention and control groups.

Secondary outcomes will include:

1) Changes in DHO and providers’ knowledge and attitudes related to IPT in both intervention and control arms over time, as measured by quantitative surveys and data from focus group discussions (FGDs) within intervention districts and Key Informant Interviews (KII) within control districts. We will compare these changes across study arms.

2) In addition, for frontline providers, we will compare measures of social influence of DHOs on their own attitudes and practices in the intervention vs. control arms. These measures include perceptions of DHO credibility, salience of information from DHOs, and level of exposure to DHO influence (via assessment of quality and quantity of communications from DHOs).

3) Additional clinical secondary outcomes will include: a) IPT completion - as measured by sufficient INH refill visits to complete 180 doses of INH in a nine-month period, recorded on IPT registry or “blue card” clinical data from clinics overseen by DHOs participating in the SPIRIT cluster randomized trial; and b) TB incidence, as measured from government TB registry data from each district. We will compare these outcomes (IPT completion and TB incidence) by study arm, within the sub-sample described for Aim 2 (below).

The schedule of evaluation for outcome measures is shown in Table 2.

Table 2. SPIRIT Trial - Schedule of Evaluations

		Baseline	2-4 Months	6 Months	12 Months	18 Months	24 Months	30 Months	36 Months

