5.7 Statistical Analysis

Overview of statistical analyses for IPT uptake: The target population for the primary outcome is all HIV+ adult (≥ 15 years) patients who are eligible for IPT within 36 months of intervention start (in each pair-matched DHO group), and in care at a facility overseen by DHOs participating in the SPIRIT trial. The analytic population for the primary outcome is all adults in active HIV care in the largest two clinics in each district of the trial. The primary outcome (Section 5.6.1 above) for each randomized group is the rate at which these patients receive a prescription for INH over the 12-36 month period following the intervention start. In the primary analysis, we will account for prior INH starts and changes in the analytic population. All DHO groups are followed for three years total.

Estimation of the impact of the SPIRIT intervention on this outcome will be based on a two-stage analysis. In the first stage we will estimate IPT uptake for each DHO group. IPT uptake will then be compared between SPIRIT intervention and control arms with targeted maximum likelihood estimation (TMLE), adjusting using a pre-specified algorithm, and accounting for the pair-matched design and limited numbers of independent units.⁴² As a secondary analysis, we will implement the unadjusted effect estimator. Hypothesis testing will be based on a two-sided test at the $\alpha=0.05$ significance level. We also propose to examine possible effect modifiers and mediators (e.g. HIV prevalence, TB screening, loss to follow-up rates, study time, drug shortages and drug availability).

Analyses of secondary quantitative outcomes (IPT completion, TB incidence: see Aim 2) will be implemented analogously.

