in which the intervention package is delivered to District Health Officers (DHOs) and District TB/Leprosy Supervisors (DTLSs), mid-level health managers who oversee health service delivery (DHOs) and TB-specific activities (DTLSs) in Uganda. The SEARCH-IPT intervention package is detailed in the Study Protocol. In brief, the social network-based, behavioral change model consists of teaching mini-collaboratives with business leadership and management training; reporting, review and discussion of IPT uptake at mini-collaborative meetings; and a two-way SMS system for DHOs/DTLSs and their front-line providers to help enable IPT uptake.

Districts randomized to the control receive no study interventions, beyond ensuring that the Ministry of Health IPT guidelines are disseminated.

Study timeline: As described elsewhere, there were many events unrelated to the study, which are likely to impact health outcomes in Phase 1. Immediately prior to study launch (end of 2017), there was a massive shortage of IPT that lasted until the end of 2018. Then starting in the third quarter of 2019 (Q3-2019), the Ministry of Health led a country-wide program to increase IPT use with support from PEPFAR (hereafter called “the 100-day IPT push”). Additionally in 2019, the Ugandan government divided select districts into two new districts. Finally, the COVID-19 pandemic began in March 2020.

To account for drug shortages and answer the most relevant scientific question, the measurement period for the main study outcomes (IPT uptake and HIV-associated TB incidence) will begin at the quarter corresponding to the first-year meeting of the mini-collaboratives, which occurred in the intervention arm only. Specifically, follow-up begins in Q1-2019 in Southwestern districts and in Q2-2019 in the Eastern and East-Central districts. All districts are followed through the close of Phase 1, and analyses will be over two years (8 quarters) of follow-up. Data from the quarter immediately preceding the follow-up period (i.e., Q4-2018 in the Southwest and Q1-2019 in the East and East-Central) are assumed to provide baseline data.

Descriptive analyses: At baseline, we will describe the study population by region (East, East-Central, and Southwest) by providing summary measures of district-level characteristics, including but not limited to

- Number of districts
- Number of participating DHOs/DTLSs
- Number of adults in active HIV care at the district-level

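### The SAP's baseline quarter falls about 9 to 12 months after intervention start, so randomisation does not justify the assumed balance in prior IPT starts, and lead-in starters stay in the person-time at risk

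*SAP*

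**What the plan says.** **Timing.** Protocol 5.6.1 measures the primary outcome over 24 months, "beginning 12 months after the intervention start in each pair-matched DHO group", and explains: "The 12-month lead-in is to account for ramp-up of the SPIRIT intervention and for INH stock-outs". SAP section 1 (Study timeline) opens follow-up in the quarter of the first-year mini-collaborative meeting: Q1-2019 in the Southwest, Q2-2019 in the East and East-Central. "Data from the quarter immediately preceding the follow-up period" (Q4-2018 and Q1-2019 respectively) serve as baseline.

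**Exposure before that quarter.** Protocol Table 2 schedules intervention-arm meetings at baseline, 2-4 months and 6 months. Protocol 5.3.1 plans twice-yearly meetings "with 1-2 additional meetings in the first year of the intervention period". The control arm has none.

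**Drug supply.** SAP section 1 records that "there was a massive shortage of IPT that lasted until the end of 2018".

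**Denominator.** SAP section 2 (Incidence rate calculations) takes all adults in active care as eligible at the start of follow-up, in every analysis. It subtracts from person-time only IPT starts made during follow-up, and supports this with: "By randomization, the number in active HIV care and the number who had previously started IPT should be balanced between arms". SAP section 3 uses parallel wording for prior TB diagnoses. Protocol 5.6.1 describes the denominator as "accounting for prior starts and other changes in the active care population", and Protocol 5.7 says "we will account for prior INH starts and changes in the analytic population".

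**Covariates.** The TMLE for the primary outcome selects among baseline IPT uptake, baseline active care size, or no adjustment. For TB incidence, baseline TB incidence replaces baseline uptake.

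**The concern.** Randomisation makes the arms comparable when they are randomised. It does not speak for events in the following year if only one arm was being encouraged to prescribe IPT. Two consequences follow for the primary analysis.

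- **Person-time.** Someone who started IPT in the lead-in is no longer at risk of starting but is counted as at risk for all eight quarters. If the intervention arm has more such people, its rate is diluted more than the control rate.
- **Adjustment.** Baseline IPT uptake may already carry part of the intervention effect. Adjusting for it can shift the estimated rate ratio.

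At stake are the size of the primary rate ratio and some power, in a trial planned at 80%. SAP section 4 takes its survey baseline at randomisation, so the word baseline has two meanings within one plan.

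**Working it through.** **1. The SAP's power figure.** Inputs from SAP 6.3: 22 v 32 per 100 person-years (PY), 7 groups per arm, k = 0.25, about 21,500 PY per group, one-sided 5%.

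c = 1 + (z_α + z_β)² × [(λ0 + λ1)/y + k²(λ0² + λ1²)] / (λ1 − λ0)²
= 1 + 6.183 × [0.54/21,500 + 0.0625 × 0.1508] / 0.01 = 6.84, so 7 groups. Power at 7 is Φ(√(6/0.945) − 1.645) = 0.81. The plan's figure reproduces.

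**2. Person-time model.** Let f be the fraction of people in care who had already started IPT when follow-up opened, and h the annual start rate among the rest. In a closed population over two years, the SAP's rule gives

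rate = (1 − f)(1 − e^(−2h)) / [(1 − f)(1 − e^(−2h))/h + 2f].

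With f = 0 this returns 0.22 and 0.32, RR 1.45. A quarter-by-quarter version agrees (1.454).

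**3. Main assumed case.** The documents give no lead-in starts by arm, so these inputs are assumptions. The shortage ended with 2018, so East/East-Central had one quarter with drug before follow-up. Take a normal control quarter there (0.22/4 = 5.5%), and 6.75% or 8% in the intervention arm (half or all of the planned effect; all is an upper case, since the protocol calls this year ramp-up). Southwest starts are near zero: 5% of normal, 0.275% in both arms.

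- East/East-Central control: 0.945 × 0.3560 = 0.3364; 0.3364/(0.3364/0.22 + 0.11) = 0.205.
- Intervention, all of the effect: 0.92 × 0.4727 = 0.4349; 0.4349/(0.4349/0.32 + 0.16) = 0.286. RR 1.395.
- Intervention, half: 0.9325 × 0.4727 = 0.4408; 0.4408/(0.4408/0.32 + 0.135) = 0.291. RR 1.420.
- Southwest: 0.2192 and 0.3186.

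Trial-wide, two Southwest weights are used because the documents do not settle one: 4 of 14 groups (Protocol 9.2.1), or 14 districts (Figure 1 legend) of an assumed 80 (the SAP's 40 control districts plus an assumed 40).

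| Southwest weight | RR, half effect | RR, all | Power, half | Power, all |
|---|---|---|---|---|
| 4/14 | 1.430 | 1.412 | 0.778 | 0.754 |
| 14/80 | 1.426 | 1.406 | 0.773 | 0.744 |

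The rate ratio is multiplied by 0.983 to 0.967, a fall of about 2-3%.

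**4. Other lead-in rates.** Here every district has the stated annual control rate through the lead-in.

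| Control lead-in rate per 100 PY | Lead-in RR | Observed RR | Power |
|---|---|---|---|
| 1 | 1.45 | 1.444 | 0.80 |
| 2 | 1.45 | 1.434 | 0.78 |
| 5 | 1.00 (balanced) | 1.446 | 0.80 |
| 5 | 1.45 | 1.403 | 0.74 |
| 10 | 1.45 | 1.356 | 0.66 |
| 10 | 2.00 | 1.26 | 0.48 |

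Even exact balance does not fully restore the ratio.

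**5. Do the planned sensitivity analyses help?** The 97.5% and 0% versions subtract fewer prior starts, so they only add person-time. In East/East-Central with all of the effect they give RR 1.392 and 1.301, against 1.395 in the primary calculation and 1.454 with lead-in starters removed.

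**6. Covariate.** This is a simulation with a linear working model as a stand-in for the TMLE: 40 v 40 districts, outcome log-SD 0.25, covariate log-SD 0.5, covariate always adjusted, true RR 1.455.

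- Baseline-quarter RR 1.10: adjusted RR 1.43 to 1.41 at correlations 0.3 to 0.7; 1.48 at −0.3.
- Baseline-quarter RR 1.45: 1.38 to 1.29 at 0.3 to 0.7; 1.53 at −0.3.

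With covariate selection added, and the step 3 lead-in assumptions at correlations 0.3 and 0.5, the multiplier is 0.996 to 0.987 with 14 group-level units and 0.987 to 0.961 with 7 + 40 units. If Southwest baseline uptake was at normal levels instead, it reaches 0.904. The correlations and variance split are assumptions throughout.

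**7. TB.** At the protocol's 200 per 100,000 PY, one lead-in year puts about 0.2% of people wrongly in the denominator.

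**The case against.** - **Balance may still hold.** The shortage ran to the end of 2018, leaving no pre-follow-up quarter with normal supply in the Southwest and one in East/East-Central. If the lead-in had no effect, the arms stay balanced. This stands: the documents do not show that the balance statement is false, only that randomisation does not justify it.
- **The protocol conflict is not clear-cut.** Protocol 5.6.1 and 5.7 promise to account for prior starts without saying prior to what. Subtracting earlier starts within follow-up can be read as compliance. This also stands, but the SAP itself raises earlier starters and sets them aside on the balance argument alone.
- **Safeguards exist.** The planned unadjusted estimator avoids the covariate issue. By-arm baseline summaries would show an imbalance in that quarter, and the Southwest stratum should be largely free of lead-in starters if the shortage kept starts near zero. But the unadjusted estimator leaves person-time as it is, the summaries cover one quarter and not the year, and the Southwest has four groups. No planned trial-wide analysis removes lead-in starters.
- **The power loss is an upper reading.** It uses 14 units without adjustment, which SAP 6.3 calls conservative; the primary analysis uses 47 units. Agreed.
- **Active care size.** A reader might infer that this covariate is equally suspect, because the rationale in Protocol section 6 says ART use could be indirectly affected. That sentence concerns ART use and explains why refills are measured in the Aim 2 subsample. It does not say that the number in care would change.

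**Conclusion.** The point holds as a matter of timing and justification. The baseline quarter is post-randomisation, the candidate covariate taken from it may already reflect the intervention, and lead-in starters remain in the denominator in every planned trial-wide analysis.

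The person-time bias is toward no effect if the intervention raised lead-in starts: about 2-3% of the rate ratio (1.45 to 1.43-1.41) under the assumed rates, and more if lead-in uptake was higher. A reader might infer that the whole problem is small and always conservative. The documents do not support that, because they give no lead-in starts by arm. The covariate effect goes toward 1 if earlier and later uptake correlate positively, and away from 1 if early uptake depletes later starters.

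A reader might also infer that a positive result would be spurious. With no effect at any time, including the lead-in, neither feature inflates type I error. That assurance concerns the test under the null, not the size of a non-null estimate.

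For TB the person-time effect is negligible, and its covariate effect was not quantified; what matters there is the wording and the timing of the covariate.

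**What to change.** 1. Drop baseline IPT uptake and baseline TB incidence from the adjustment candidates, or take them from a quarter before intervention start. Counting back 12 months from follow-up, those quarters are about Q4-2017 (Southwest) and Q1-2018 (East/East-Central), at or inside the shortage, so dropping is simpler. Baseline active care size can stay.
2. Add a trial-wide analysis that also subtracts IPT starts between intervention start and follow-up start, under the existing retention rule, and report those starts by arm.
3. Show the already planned unadjusted estimate beside the primary one.
4. In SAP sections 2 and 3, replace the appeal to randomisation with a statement that balance is assumed and will be checked.

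SAP 6.1 records that version 1.0 was locked before unblinding and version 2.1 before manuscript submission. If the data are already unblinded, keep the locked primary analysis and label items 1 and 2 as sensitivity analyses.

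Cost: an extract of the lead-in quarters (and the pre-start quarter if used) from the same HMIS source, two reworded sentences and a few extra analyses. Some precision may be lost without the covariate. Because HMIS cannot separate a missing IPT count from zero, lead-in starts will be a lower bound and the correction may be incomplete.
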